# Secondary objective 3: To describe treatment patterns in patients with NHL or CLL who receive treatment with rapidly infused CT-P10.

- Summary measures of the following CT-P10 treatment parameters:
  - Number of infusions
  - o Duration of infusions
  - Starting and subsequent doses
  - Chemotherapy regimen given with CT-P10 (if applicable) and premedications received
  - o Time on treatment
  - Reason why treatment was discontinued (if applicable)
- Distribution of subsequent treatment regimens (after discontinuation of CT-P10).

- For CT-P10 treatment (in the post-index period):
  - o Date of each infusion.
  - Pre-medications given.
  - Treatment doses given (actual and per m²).
  - o Duration of each infusion.
  - Name of chemotherapy regimen given with CT-P10.
  - Treatment discontinuation date (the date of discontinuation will be defined as the date of the last dose / infusion) or ongoing.
  - Treatment ongoing at 6 months post-index (Yes / No / not known).
  - Reason for permanent discontinuation (adverse event, death, disease progression, completed course of treatment, budget constraints, other).
- Name, type and start date of subsequent treatment regimens (after discontinuation of CT-P10).

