## 2.2 Key definitions

- **Index event:** first rapid infusion of CT-P10 (note: first rapid infusion must have been given as part of the second or a subsequent treatment cycle).
- **Index date:** date of first rapid infusion of CT-P10 (note: first rapid infusion must have been given as part of the second or a subsequent treatment cycle) (day 1).
- **Rapid infusion:** defined as a total infusion time for CT-P10 of 90 minutes or less.
- **Infusion-related reaction (IRR):** any adverse event (AE) from a pre-defined list (see Annex 3) occurring on day 1 or day 2 after an infusion of CT-P10.
- Pre-index observation period: the pre-index observation period for this study
  will be from the date of diagnosis of NHL or CLL until the index date, and will be
  used to capture patients' demographic and clinical characteristics.
- Post-index observation period: patients will be observed for a period of 6
  months after the index date (or until death, if sooner), to capture safety and
  clinical outcomes.
- Adverse event (AE): An AE is any untoward medical occurrence in a patient administered a pharmaceutical product and which does not necessarily have to have a causal relationship with this treatment. An AE can therefore be any unfavourable and unintended sign (including an abnormal laboratory finding, for example), symptom, or disease temporally associated with the use of a medicinal product, whether or not considered related to the medicinal product. The definition of an AE includes worsening of a pre-existing medical condition.

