# 8.4 Secondary research objectives

To describe the following in patients who receive rapid infusion of CT-P10 for the treatment of NHL or CLL:

1. Safety profile in the 6 months post-index date (index date defined as the date of the first rapid infusion of CT-P10, which must have been given as part PASS PT Celltrion RAPID v2 0 FINAL 18APR2018

Page 19 of 43

of the second or a subsequent treatment cycle), including incidence (and frequency per patient per month, where appropriate) of the following safety events: IRRs, grade 3 or grade 4 IRRs, any adverse event (AE), any serious adverse event (SAE), any grade 3 or grade 4 AE, AEs as the primary cause for treatment discontinuation.

- 2. Clinical effectiveness in the 6 months post-index date (to be analysed separately for NHL and CLL), including overall survival (OS), progression free survival (PFS), best response, overall (complete/partial) response rate, time to complete or partial response.
- 3. NHL / CLL treatment patterns during the observation period (from diagnosis of NHL or CLL to 6 months post-index date), including types and doses of treatment, number and duration of infusions, time on treatment and reasons for discontinuation.
- 4. Patients' demographic, clinical, and NHL/CLL disease characteristics.

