# Secondary objective 4: To describe the baseline demographic, clinical and disease characteristics of patients with NHL or CLL who receive treatment with rapidly infused CT-P10.

Demographic and clinical characteristics (at index date unless specified)

- Summary measures of patients' age, sex, ethnicity, employment status, comorbidities (Charlson Comorbidity Index ), disease duration and prior chemotherapy and rituximab exposure.
- Number of other diagnosed malignancies.
- Summary of Eastern Cooperative Oncology Group (ECOG) performance status at closest time point prior to the index date.
- Summary measures of duration of CT-P10 infusion(s) given prior to the index event.
- Proportion of patients who experienced IRRs with CT-P10 infusion(s) given prior to the index event (by IRR grade).

- Month and year of birth
- Index date
- Date of diagnosis of NHL or CLL
- Sex (male/female)
- Ethnicity
- Employment status (full time / part time / unemployed / student / retired / home-maker) at closest time point prior to index date and date documented.
- Relevant comorbidities ongoing at index date (components of Charlson Comorbidity Index will be captured)
- Prior treatment regimens for NHL or CLL from diagnosis of NHL or CLL to the index date (name and type of treatment, start date, stop date [for

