# most recent regimen and most recent rituximab only]).

- Other malignancies diagnosed prior to the index date.
- ECOG score at closest time point prior to the index date and date of assessment.
- Date and duration of any CT-P10 infusion(s) given prior to the index event and description / CTCAE v4 grade of any IRRs experienced.

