#### 9.7.2 Secondary analyses

For the secondary endpoint safety analyses, rates of events per-patient-per month will be reported. Secondary clinical effectiveness endpoints will be reported separately for patients with NHL or CLL. The time-to-event clinical effectiveness endpoint analyses (OS, PFS, time to complete or partial response) and CT-P10 treatment duration will be displayed descriptively using Kaplan Meier plots from the index event until the date of the event or censoring. Patients who are known to be alive at 6 months post-index will be censored on that date for OS whereas patients who are lost to follow-up will be censored at the date they were last known to be alive (i.e. the last recorded hospital visit within the 6 months post-index). For PFS, patients will be censored on the date they were last known not to have disease progression (i.e. the date of last documented response assessment) and for time to complete or partial response, patients will be censored at the date of the last recorded known response. For treatment duration, censoring will occur at the 6 months post-index date (if CT-P10 treatment is known to be ongoing at 6 months) or the date of the last infusion (if the patient is lost to follow-up). Absolute counts and the percentages of these events occuring in each disease indication group will be reported. Survival rates for 6 months post NHL or CLL diagnosis will also be calculated. Summary data will be tabulated and also displayed graphically where appropriate.

The proportion of patients assessed as having a best response of complete response, partial response, stable disease or progressive disease within the 6 months post-index based the documented assessment of the local investigator and the proportion of patients with a complete or partial response, will be presented with 95% CI.

For the demographic, clinical, and NHL/CLL disease characteristics endpoint analyses, the study population will be described by means of summary statistics. Distributions and descriptive statistics of both central tendency (medians and means) and dispersion (standard deviation, interquartile range [IQR]) will be presented for

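### CT-P10 dose and premedication are listed only for the post-index period, so the starting dose promised under objective 3 is not recorded, and the treatment-duration plot shows time from first rapid infusion

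*Protocol*

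**What the plan says.** Protocol Section 8.4 sets objective 3 as describing treatment patterns "during the observation period (from diagnosis of NHL or CLL to 6 months post-index date), including types and doses of treatment", along with number and duration of infusions and time on treatment. Section 9.7.2 repeats that treatment patterns are described over the whole study period.

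Section 9.3 turns this into endpoints and variables:

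- The dose endpoint is "Starting and subsequent doses". Time on treatment and premedications are also listed as endpoints, with no qualification as to when they start.
- The dose variable is "Treatment doses given (actual and per m²"). It and the premedication variable stand under "For CT-P10 treatment (in the post-index period").
- For CT-P10 before the index, the variables under objective 4 are "Date and duration of any CT-P10 infusion(s) given prior to the index event and description / CTCAE v4 grade of any IRRs experienced".
- Prior regimens are also taken under objective 4: "Prior treatment regimens for NHL or CLL from diagnosis of NHL or CLL to the index date (name and type of treatment, start date", with stop dates for the most recent ones. No dose is included.

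Section 2.2 fixes the index: the "first rapid infusion must have been given as part of the second or a subsequent treatment cycle". Section 9.7.2 says that "CT-P10 treatment duration will be displayed descriptively using Kaplan Meier plots from the index event until the date of the event or censoring".

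**The concern.** The objective and the variable list cover different periods. The objective reaches back to diagnosis, while the dose and premedication variables begin at the index, which by definition is not the first cycle. An abstractor who follows Section 9.3 exactly would hand the analyst a first recorded dose from cycle 2 or later. Under the present endpoint name, that dose would be reported as the starting dose.

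The duration analysis has a related but lesser fault. The endpoint is called time on treatment, but the plot measures from the first rapid infusion. Centres may differ in the cycle at which they begin rapid infusion, and Section 9.7 pools all centres. The pooled curve would then partly reflect when patients were switched and partly how long they were treated. A reader who takes it as total CT-P10 exposure would be misled.

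**Working it through.** The protocol states no figure for either item, so there is nothing to reproduce. The check sets the variable lists side by side and then illustrates the size of the duration gap.

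**Step 1. What is listed, by period (Section 9.3, objectives 1, 3 and 4).** I read the post-index period as including the index infusion itself.

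| Item | CT-P10 infusions before the index | Index infusion and later |
|---|---|---|
| Infusion date | listed | listed |
| Infusion duration | listed | listed |
| Infusion-related reactions | listed, with grade | listed, with grade |
| Chemotherapy regimen | name, type and start date, through prior regimens | name listed |
| Dose | **not listed** | listed |
| Premedication | **not listed** | listed |

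The gap is therefore dose and premedication. Number and duration of infusions can be completed for the whole period, and regimen names are covered.

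**Step 2. Can the gap be filled without a protocol change?** Section 9.3 says it sets out the variables to be collected and leaves only response options to the data collection form. Section 10 limits collection to what the planned analyses require. Pre-index doses should therefore not be expected in the database, and a statistical analysis plan cannot supply data that were not abstracted.

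**Step 3. Who is affected?** Every patient with at least one CT-P10 infusion before the index. Section 9.2.1 excludes reference rituximab in earlier cycles of the same line, so CT-P10 is the likely product in those cycles. It does not expressly require CT-P10 in cycle 1, and the pre-index variable refers to any such infusion. The exact share of the 300 is unknown.

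**Step 4. Size of the duration difference (illustration).** Take n equally spaced infusions, L days apart, with the index at cycle k. None of n, L or k is given in the protocol.

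- First to last infusion: (n − 1) × L
- Index to last infusion: (n − k) × L
- Difference: (k − 1) × L, a share of (k − 1)/(n − 1)

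| n | L (days) | k | First to last | Index to last | Omitted | Share |
|---|---|---|---|---|---|---|
| 6 | 21 | 2 | 5 × 21 = 105 | 4 × 21 = 84 | 21 | 1/5 = 20% |
| 6 | 21 | 4 | 5 × 21 = 105 | 2 × 21 = 42 | 63 | 3/5 = 60% |
| 8 | 14 | 2 | 7 × 14 = 98 | 6 × 14 = 84 | 14 | 1/7 = 14% |
| 8 | 28 | 4 | 7 × 28 = 196 | 4 × 28 = 112 | 84 | 3/7 = 43% |

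Over L from 14 to 28 days, n of 6 or 8 and k from 2 to 4, the plot omits 14 to 84 days, or 14% to 60% of the time from first to last infusion.

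**Step 5. Is that interval lost?** No. The pre-index infusion dates are collected, as are every later infusion date and the discontinuation date, which Section 9.3 defines as the date of the last infusion. Regimen start dates allow earlier infusions to be assigned to their line. The full duration follows by subtraction.

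**The case against.** The strongest reply has four parts.

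- **The index is the natural origin.** Section 9.3 defines the exposure of interest as CT-P10 by rapid infusion in the second or a later cycle. A patient enters the study only by reaching that infusion, so earlier time is free of discontinuation by construction. Section 9.7.2 states the origin openly, and its separate summary of duration on treatment is not tied to the index. This stands as a defence of the plot. It does not settle what the unqualified endpoint in Sections 8.4 and 9.3 means, and the two should be matched.
- **Starting dose could mean the dose at the first rapid infusion.** The protocol never says so, and both objective 3 and Section 9.7.2 point to the whole period. If that is the intent, a change of name is enough.
- **The gap could be repaired later.** Section 9.1 allows abstraction in batches, Section 9.6 resolves queries against source records, and Section 10 keeps a patient log at each centre. So a reader should not infer that the doses are lost for good. Returning to charts in five countries is still dearer than adding fields beforehand.
- **The item is minor.** It is a descriptive part of the third secondary objective. This is correct and limits the weight of the point.

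A reader might also infer that time on treatment cannot be reported correctly, or that all 300 patients are affected. The documents support neither: the dates needed are collected, and prior CT-P10 is implied but not required.

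**Conclusion.** The point holds in two parts of unequal weight.

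- **Dose and premedication.** This is a genuine mismatch between objective and data. For every patient with CT-P10 before the index, no listed variable gives the starting dose or the premedication for those infusions. I expect this to be most patients, on the assumption that earlier cycles of the line used CT-P10.
- **Time on treatment.** The time origin does not match the endpoint's name, but no data are missing. The planned plot shows time from first rapid infusion. The 14 to 84 days are illustrations under assumed cycle lengths, numbers of infusions and index cycles.

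The primary endpoint, the post-index safety rates and the survival and response endpoints are untouched. The change is worth making because objective 3 cannot be answered as written and the remedy is small.

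**What to change.** For dose, do one of the following:

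- add dose (actual and per m²) and premedication to the record for pre-index CT-P10 infusions in the same line; or
- rename the endpoint as dose at and after first rapid infusion, and narrow objective 3 in Section 8.4, the endpoint list in Section 9.3 and the text of Section 9.7.2 to match. Premedication would need the same restriction.

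For duration, do one of the following:

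- summarise time on treatment from the first CT-P10 infusion of the line, using the dates already collected; if this is shown as a Kaplan-Meier curve, patients should enter the risk set at the index date, because they could not have been included had they stopped earlier; or
- keep the index origin and label the analysis as time from first rapid infusion.

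Regimen need not be added, since prior regimen names are already collected. The cost is a few fields on infusion records that sites already open for date, duration and reactions, with slightly more abstraction per patient. The renaming options cost only wording, but give up the description of dose before the index.

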# Secondary objective 4: To describe the baseline demographic, clinical and disease characteristics of patients with NHL or CLL who receive treatment with rapidly infused CT-P10.

Demographic and clinical characteristics (at index date unless specified)

- Summary measures of patients' age, sex, ethnicity, employment status, comorbidities (Charlson Comorbidity Index ), disease duration and prior chemotherapy and rituximab exposure.
- Number of other diagnosed malignancies.
- Summary of Eastern Cooperative Oncology Group (ECOG) performance status at closest time point prior to the index date.
- Summary measures of duration of CT-P10 infusion(s) given prior to the index event.
- Proportion of patients who experienced IRRs with CT-P10 infusion(s) given prior to the index event (by IRR grade).

- Month and year of birth
- Index date
- Date of diagnosis of NHL or CLL
- Sex (male/female)
- Ethnicity
- Employment status (full time / part time / unemployed / student / retired / home-maker) at closest time point prior to index date and date documented.
- Relevant comorbidities ongoing at index date (components of Charlson Comorbidity Index will be captured)
- Prior treatment regimens for NHL or CLL from diagnosis of NHL or CLL to the index date (name and type of treatment, start date, stop date [for

# most recent regimen and most recent rituximab only]).

- Other malignancies diagnosed prior to the index date.
- ECOG score at closest time point prior to the index date and date of assessment.
- Date and duration of any CT-P10 infusion(s) given prior to the index event and description / CTCAE v4 grade of any IRRs experienced.

#### NHL / CLL disease characteristics

- Summary of diagnosis (including type of NHL [FL / diffuse large B-cell lymphoma, DLBCL])
- Summary of NHL or CLL stage as documented in the medical records (e.g. Lugano or Ann Arbor [I, II, III, IV] for NHL, Binet [A, B, C] for CLL) at initial diagnosis and at index date.
- Summary measures (at the index date) of:
  - International Prognostic Index (IPI) score for DLBCL (as documented or calculated from component parts)
  - Follicular lymphoma (FL)IPI for FL (as documented or calculated from component parts)
  - Lactate dehydrogenase (LDH), presence of B-symptoms (unexplained fever [temperatures above 100.4°F or 38°c; unexplained weight loss of more than 10% of original body weight during the last 6 months; drenching night sweats) and bone marrow involvement for NHI
  - Tumour bulk (largest tumour diameter) and total number of tumour sites
  - Extra-nodal status

NHL / CLL disease characteristics:

- Diagnosis (FL/DLBCL/CLL)
- NHL stage as documented in the medical records (e.g. Lugano or Ann Arbor [I, II, III, IV]) and date of assessment (at initial diagnosis and closest prior to index date)
- CLL stage (Binet A, B, C) and date of assessment (at initial diagnosis and closest prior to index date).
- Result and date of assessment for the following (closest prior to index date):
  - IPI score (for DLBCL)
  - o FLIPI (for FL)
  - o LDH
  - Haemoglobin (part of FLIPI)
  - Presence of B symptoms (for NHL)
  - Bone marrow involvement (for NHL)
  - Largest tumour diameter and number of tumour sites
  - Number of extra-nodal sites

#### 9.4 Data sources

All data for the study will be sourced from patients' hospital medical records (paper and/or electronic, as applicable locally), infusion records and other local databases or electronic systems. Data will be collected either by an external researcher or a member of the patients' direct care team (to be agreed in each country before data collection commences).

All data will be collected in pseudonymised form; patients will be identified in study records by a unique study code to preserve patient confidentiality, while allowing data management queries to be raised.

## 9.5 Study size

The proposed sample size for this study is 300. Given that the study is primarily descriptive, aiming to characterise the IRR rate in patients receiving rapid infusion of CT-P10, assessments of the utility of this sample size is primarily based on the precision with which rates can be estimated. The mean frequency/incidence of IRRs for rapidly infused rituximab across a range of studies was reported to be 8.84% (95% confidence interval [CI]: 7.12 to 10.81) in a meta-analysis by Polwart. Given this, 95% CIs around estimates of possible IRRs for rapidly infused CT-P10 at different sample sizes are given below:

IRR %	200 patients		250 patients		300 patients		350 patients		400 patients	
	95% LCI	95% UCI								
8%	4.6%	12.7%	5.0%	12.1%	5.2%	11.7%	5.4%	11.4%	5.5%	11.1%
9%	5.4%	13.9%	5.8%	13.3%	6.0%	12.8%	6.2%	12.5%	6.4%	12.2%
10%	6.2%	15.0%	6.6%	14.4%	6.8%	14.0%	7.1%	13.6%	7.2%	13.4%
12.5%	8.3%	17.9%	8.7%	17.2%	9.0%	16.8%	9.2%	16.4%	9.4%	16.1%
15%	10.4%	20.1%	10.8%	20.0%	11.2%	19.6%	11.4%	19.2%	11.6%	18.9%
20%	14.7%	26.2%	15.2%	25.5%	15.6%	25.0%	15.9%	24.6%	16.2%	24.3%
30%	23.7%	36.9%	24.4%	36.1%	24.9%	35.5%	25.2%	35.1%	25.5%	34.8%

Assuming the rate of IRRs in patients receiving rapid infusion of CT-P10 are similar to those found in previous rituximab studies (rounding to 10%), we can expect the 95% CIs to be between 6.8 and 14.0% with a sample size of 300; a 95% CI width of 7.2%. If the sample size for the study was increased by 100 patients, the gain in precision would be a 95% confidence interval width of 6.2%, while for 200 patients the width would increase to 8.8%. The highest IRR rates among the studies investigated by Polwart gave an IRR rate of approximately 30%. For this IRR rate the 95% confidence interval would span between 24.9 and 35.5% for a sample of 300. Given the diminishing returns of the effect of increasing study sample size on the precision of estimates derived, a sample of 300 patients is considered acceptable.

The expected sample size split for patients with NHL and CLL is based on the epidemiology of both diseases, with approximately 76,800^17 and 20,200^18 patients

with NHL and CLL, respectively, being alive at the end of 2010 in the UK. Based on these prevalence estimates, and assuming a similar prevalence across Europe, it is expected that the sample will comprise approximately 240 patients with NHL and 60 with CLL.

## 9.6 Data management

Data management and handling of data will be conducted according to the study specific data management plan (DMP) and pH Associates standard operating procedures (SOPs). Data will be collected via an electronic data capture (EDC) system using a standardised electronic data collection form (eDCF) designed specifically for the study. Before the start of data collection, site staff collecting data from patients' hospital medical records will be trained in data entry into the eDCFs by study management staff and consistency checks will be built into the eDCF to ensure data quality.

Data management for eDCFs will be carried out using MACRO™, a data management system which has a secure web-based data entry interface and is fully validated and compliant with Food and Drug Administration (FDA) Information Governance standard 21 Code of Federal Regulations (CFR) part 11. The MACRO™ system has restricted access permissions for data entry management and analysis and maintains an audit trail of all changes to data and activity in the system in line with 21 CFR part 11. If corrections are needed to an eDCF, queries will be raised in the EDC system by the study data manager and these will be resolved by the responsible investigator (or designee) by reference to the source records.

